**Table 6–1 Safety Laboratory Evaluations**

Visit	Tests
Visit 1 (Baseline)	CHEM, CBC, UA, urine toxicology screen and dipstick, urine pregnancy test
Visit 2 (Week 2)	Urine pregnancy test
Visit 3 (Week 6)	Urine pregnancy test
Visit 4 (Week 12)	CHEM, CBC, UA, urine pregnancy test
Visit 5 (Week 20)	Urine pregnancy test
Visit 6 (Week 28)	CHEM, CBC, UA, urine pregnancy test
Visit 7 (Week 36)	Urine pregnancy test
Visit 8 (Week 44)	CHEM, CBC, UA, urine pregnancy test
Visit 9 (ET/EOT)	CHEM, CBC, UA, urine toxicology screen, urine pregnancy test

Abbreviations: CBC=complete blood count; CHEM=clinical chemistry serum tests; EOT=end of treatment; ET=early termination; UA=urinalysis

#### **6.4.5 Syncope**

At each study visit, the investigator should query the caregiver for occurrences of syncope since the last visit. An occurrence of syncope should be reported as an adverse event. If the caregiver reports an occurrence of syncope, the investigator should ask the “syncope adverse event questions” in [Appendix G](#).

#### **6.4.6 Somnolence**

At each study visit, the investigator should query the caregiver for occurrences of somnolence since the last visit. An occurrence of somnolence should be reported as an adverse event. If the caregiver reports an occurrence of somnolence, the investigator should ask the “somnolence adverse event” questions in [Appendix H](#).

## 6.5 Blood Sampling

The involvement of experienced personnel in the conduction of blood drawing in this population is strongly recommended.

During blood sampling, measures to reduce pain are encouraged and can include application of numbing medication (e.g., lidocaine/prilocaine cream) to the draw site and/or use of a winged infusion set (i.e., a “butterfly” needle). Mild sedation is allowed exceptionally for blood draws (e.g., alprazolam at a pediatric-appropriate dose per age, and the *lowest dose* deemed necessary by the Investigator) just in cases when the subject’s agitation/anxiety does not allow a safe and accurate measurement and the Investigator, with agreement from the caregiver, considers it safe and appropriate for the subject.

The total amount of blood to be obtained from each subject for safety laboratory blood samples during the course of this study will not exceed approximately 40 mL (6- through 17-year-olds) and 31.1 mL (5-year-olds). Note: this total amount does not account for additional blood samples that may be collected (e.g., to verify elevated laboratory results, etc.).

[Table 6–2](#) tabulates the maximum allowable blood collection volumes by weight for affected children and [Table 6–3](#) and [Table 6–4](#) summarize the blood volumes to be drawn from 6-through 17-year-olds and 5-year-olds, respectively, in both a 24-hour and a 30-day period. The total amount of blood to be obtained from each subject should not exceed the allowable limits for affected children.

**Table 6–2 Blood Collection Volume Limits in Affected Children**

Weight	14 kg	15 kg	16 kg	17 kg
Maximum allowable blood volume in a 24-hour period	28 mL	30 mL	32 mL	34 mL
Maximum allowable blood volume in a 30-day period	56 mL	60 mL	64 mL	68 mL

Sources: North Shore LIJ Human Subject Protection Program Guidance Document, Maximum Blood Draw Limits, Version 11/24/14; National Center for Health Statistics (CDC) 2-20 years: Stature-for-age and weight-for-age percentiles

Notes: 5th percentile body weight for 5 year old girls≈14.6 kg; 5th percentile body weight for 5 year old boys≈15.1 kg.

**Table 6–3** **Blood Collection Volumes for Safety Labs (6- through 17-year-olds)**

	Baseline Visit	Visit 4 (Week 12)	Visit 6 (Week 28)	Visit 8 (Week 44)	Visit 9 (Week 52)
Total safety labs each study visit	8 mL	8 mL	8 mL	8 mL	8 mL
Total volume in any 24-hour period	8 mL	8 mL	8 mL	8 mL	8 mL
Total volume in any 30-day period					
Baseline	8 mL	--	--	--	--
Week 12	--	8 mL	--	--	--
Week 28	--	--	8 mL	--	--
Week 44	--	--	--	8 mL	--
Week 52	--	--	--	--	8 mL

**Table 6–4** **Blood Collection Volumes for Safety Labs (5-year-olds)**

	Baseline Visit	Visit 4 (Week 12)	Visit 6 (Week 28)	Visit 8 (Week 44)	Visit 9 (Week 52)
Total safety labs each study visit	5.9 mL	6.3 mL	6.3 mL	6.3 mL	6.3 mL
Total volume in any 24-hour period	5.9 mL	6.3 mL	6.3 mL	6.3 mL	6.3 mL
Total volume in any 30-day period					
Baseline	5.9 mL	--	--	--	--
Week 12	--	6.3 mL	--	--	--
Week 28	--	--	6.3 mL	--	--
Week 44	--	--	--	6.3 mL	--
Week 52	--	--	--	--	6.3 mL

## 6.6 Safety Follow-up

A 30-day safety follow-up telephone contact is to be completed for subjects who complete the treatment period of the study, as well as those who discontinue prematurely from the study. Subjects should have the following completed at 30(+3) days after last dose of study drug:

- Assessment of concomitant medications/treatments
- Assessment of AEs
- Assessment of syncope

- Assessment of somnolence

## 6.7 Unscheduled Visits

Unscheduled visits may occur as determined by the Investigator. The following safety assessments generally should be recorded at each unscheduled visit: assessment of AEs, assessment of syncope, assessment of somnolence, assessment of concomitant medications/treatments, measurement of vital signs and weight, the ESRS-A, and completion of the C-SSRS. The Investigator may perform any additional safety evaluations deemed by the Investigator to be clinically indicated.

## 6.8 Remote Assessments or Visits

Circumstances may arise (e.g., pandemic, natural disaster, political upheaval, or to minimize subject and caregiver burden) when on-site assessments of efficacy and/or safety are not possible. In those cases, assessments may be performed offsite by raters either in person, or via video technology or telephone where possible. For all visits that are conducted remotely, the Investigator **must** contact the Medical Monitor for approval of the plan. Sites must keep a log to identify details of all visits that are administered remotely. For some remote efficacy assessments the vendor will provide additional training to ensure calibration to reduce discrepancy between on-site and remote assessments (ABC, CGI-S, RBS-R, VABS-Socialization).

Provided that the subject is physically in the clinic, and accompanied by a relative, all caregiver-rated assessments may be provided remotely.

# 7 ADVERSE EVENTS

## 7.1 Specification of Safety Parameters

### 7.1.1 Definition of Adverse Event

An AE is defined as “any untoward medical occurrence in a patient or clinical study participant, temporally associated with the use of study drug, whether or not considered related to study drug”.

An AE can therefore be any unfavorable and unintended sign (e.g., an abnormal laboratory finding), symptom, or disease temporally associated with the use of a drug, without any judgment about causality or seriousness. An AE can arise from any use of the drug (e.g., off-label use, use in combination with another drug) and from any route of administration, formulation, or dose, including an overdose.

A suspected adverse reaction is any AE for which there is a reasonable possibility that the drug caused the AE.

AEs do not include the following:

- Stable or intermittent chronic conditions (such as myopia requiring eyeglasses) that are present prior to Baseline and do not worsen during the study
- Medical or surgical procedures (e.g., surgery, endoscopy, tooth extraction, transfusion), or scheduled surgery/procedure. The condition that leads to the procedure is an AE if not present at time of consent.
- Overdose of concomitant medication without any signs or symptoms will not be considered an AE, but if a subject is hospitalized or has other serious criteria, the overdose will be considered an AE and shall be reported on the Sponsor's Overdose Reporting form.
- Hospitalization for elective surgery planned prior to study (situation where an untoward medical occurrence has not occurred)
- Pregnancy will not be considered an AE, but if it occurs, it will be reported on a pregnancy form

### **7.1.2 Definition of Serious Adverse Event**

In addition to the severity rating, each AE will be classified by the Investigator as “serious” or “not serious.” The seriousness of an event will be defined according to the applicable regulations and generally refers to the outcome of an event. An SAE is one that meets one or more of the following:

- Is fatal
- Is life threatening
- Results in disability or permanent damage
- Requires hospitalization (initial or prolonged)
- Results in congenital anomaly or birth defect
- Other serious event (medically significant/important medical event)

#### **Definition of Life Threatening**

A life threatening event places the subject at immediate risk of death from the event as it occurred. This does not include an AE, which, had it occurred in a more severe form, might have caused death.

#### **Definition of Hospitalization**

Hospitalization is defined by the Sponsor as a full admission to the hospital for diagnosis and treatment. This includes prolongation of an existing inpatient hospitalization.

Examples of visits to a hospital facility that do **not** meet the serious criteria for hospitalization include:

- Emergency room visits (that do not result in a full hospital admission)
- Outpatient surgery
- Preplanned or elective procedures
- Protocol procedures
- Social hospitalization, defined as admission to the hospital as a result of inadequate family support or care at the subject's primary residence

### **Definition of Disability or Permanent Damage**

Disability is defined as a persistent or significant incapacity or substantial disruption of the ability to conduct normal life functions.

### **Definition of Medically Significant**

Important medical events (medically significant events) that may not result in death, be life threatening, or require hospitalization may be considered to be an SAE when, based upon appropriate medical judgment, they may jeopardize the subject or may require medical or surgical intervention to prevent one of the outcomes listed in this definition. Examples of such events are intensive treatment in an emergency room or at home for allergic bronchospasm, blood dyscrasias, convulsions that do not result in hospitalization, or development of drug dependency or drug abuse.

An SAE may also include any other event that the Investigator or Medical Monitor judges to be serious or that suggests a significant hazard, contraindication, side effect, or precaution.

## **7.2 Classification of an Adverse Event**

### **7.2.1 Severity of Event**

The severity of each AE will be assessed as described below and reported in detail as indicated on the eCRF:

- **Mild:** awareness of sign or symptom but easily tolerated, causing minimal discomfort, and not interfering with normal everyday activities
- **Moderate:** sufficiently discomforting to interfere with normal everyday activities
- **Severe:** incapacitating and/or preventing normal everyday activities

### **7.2.2 Relationship to Study Drug**

The causality of each AE should be assessed and classified by the Investigator as “related” or “not related.” An event is considered related if there is a reasonable possibility that the event may

have been caused by the product under investigation (i.e., there are facts, evidence, or arguments to suggest possible causation).

#### **Consider the following when assessing causality:**

- Temporal associations between the agent and the event
- Response to drug cessation (de-challenge) or re-challenge
- Compatibility with known class effect
- Known effects of concomitant medications
- Pre-existing risk factors
- A plausible mechanism
- Concurrent illnesses
- Past medical history

#### **7.2.3 Duration**

The start and stop dates for AEs will be recorded using the following criteria:

- **Start:** Date of the first episode of the AE or date of worsening in severity
- **Stop:** Date when AE recovered or resolved, recovered or resolved with sequelae, or worsened in severity

#### **7.2.4 Frequency**

The frequency of the AE should be indicated according to the following definitions:

- **Single:** Experienced once, without recurrence at same severity
- **Recurrent:** More than one discrete episode with the same severity

#### **7.2.5 Action Taken With Study Drug**

- **Dose not changed:** No change in study drug
- **Dose increased:** Study drug dose increased (can only be done up to and including Week 20 visit)
- **Dose reduced:** Study drug dose reduced (can only be done up to and including Week 20 visit)
- **Drug interrupted:** Study drug temporarily stopped
- **Drug withdrawn:** Study drug discontinued permanently
- **Not applicable**
- **Unknown**

## 7.2.6 Therapy

- **None:** No new treatment instituted
- **Medication:** New treatment initiated as a direct result of AE
- **Other:** Other action required

## 7.2.7 Outcome

- **Recovered/resolved:** Recovered or resolved
- **Recovered/resolved with sequelae:** Recovered or resolved with sequelae
- **Not recovered/not resolved:** Not recovered or not resolved
- **Fatal:** Death due to an AE
- **Unknown:** Unknown

## 7.2.8 Seriousness

- **Not serious**
- **Serious** (see [Section 7.1.2](#))

## 7.2.9 Definition of Unexpectedness

An AE, the nature or severity of which is not consistent with the information provided in the Reference Safety Information section of the current pimavanserin Investigator's Brochure.

## 7.3 Time Period and Frequency for Event Assessment and Follow-up

Adverse events will be recorded from the first dose of open-label study drug through the study safety follow-up period. All ongoing AEs from the antecedent double-blind study will be carried over and recorded from Baseline for the ACP-103-070 study until resolution or the follow-up safety assessment. If an AE is ongoing at the end of the study safety follow-up period, every reasonable attempt should be made to follow and appropriately treat the subject until the AE resolves or until the Investigator deems the AE to be chronic or stable.

In the event that a subject discontinues from the study and has an ongoing AE at the time of discontinuation ([Section 4.5.1](#)), the subject should be followed and appropriately treated until the AE resolves or until the Investigator deems the AE to be chronic or stable. If a subject withdraws from the study because of an AE, no additional assessments may be performed ([Section 4.4](#)).

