#### **4.4 Subject Withdrawal of Consent**

In accordance with the Declaration of Helsinki and other applicable regulations, a subject has the right to withdraw from the study at any time, and for any reason, without prejudice to his or her future medical care.

If the subject (and/or parent/LAR) decides to withdraw consent from all components in the study, this must be documented and no additional assessments will be performed. The Sponsor may retain and continue to use any data collected before such a withdrawal of consent. The subject may request destruction of any samples taken and not tested, prior to their withdrawal of consent, and the Investigator must document this in the site study records.

If the subject (and/or parent/LAR) wants to discontinue treatment and agrees to the evaluations specified at the EOT/ET visit and/or at safety follow up (whichever is applicable), as outlined in [Table S-1](#), the agreed assessments should be conducted. The subject's reason for wanting to discontinue treatment and the agreement to continue with the applicable assessments for study termination must be documented.

Every reasonable effort should be made to keep the same parent/LAR or designee who completed the observer's study scales in study ACP-103-069 to complete them throughout study ACP-103-070 in order to maintain the validity of the scoring.

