#### **4.5 Subject Discontinuation**

Subjects may be discontinued from the study treatment for a number of reasons, including, but not limited to, those listed below:

- Adverse event
- Death
- Lack of efficacy
- Lost to follow-up ([Section 4.6](#))
- Non-compliance with study drug
- Physician decision
- Pregnancy
- Protocol deviation

- Study terminated by sponsor
- Use of prohibited medication
- Withdrawal of consent by subject (or by parent/LAR)
- Other

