#### **4.5.1 Handling of Subject Discontinuation During the Treatment Period**

Unless the subject (or parent/LAR) has withdrawn consent from all components of the study, every reasonable effort should be made to complete Visit 6/ET and the safety follow-up visit (as outlined in [Table S-1](#)) if a subject discontinues prematurely during the treatment period of the study. All information will be reported on the applicable pages of the electronic case report form (eCRF).

If a subject is discontinued from the study treatment because of an AE, every reasonable attempt should be made to follow and appropriately treat (or refer for treatment) the subject until the AE resolves or until the Investigator deems the AE to be chronic or stable. For subjects who continue to be followed for safety, serious adverse events (SAEs) should continue to be reported as described in [Section 7.4.2](#). All SAEs will continue to be followed and appropriately treated until such events have resolved or the Investigator deems them to be chronic or stable.

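### The last sentence of Protocol 7.3 is misworded: it stops all assessments after withdrawal because of an AE, without limiting this to withdrawal of consent from all components

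*Protocol*

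**What the plan says.** Section 7.3 sets the rules for recording and following AEs. Its last sentence reads: "If a subject withdraws from the study because of an AE, no additional assessments may be performed", with a reference to Section 4.4. The sentence before it, which refers to Section 4.5.1, covers a subject who discontinues from the study with an AE still ongoing and says "the subject should be followed and appropriately treated until the AE resolves or until the Investigator deems the AE to be chronic or stable".

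The other rules on when assessments stop are these:

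- **Section 4.4, full withdrawal.** Where the subject or parent/LAR "decides to withdraw consent from all components in the study, this must be documented and no additional assessments will be performed".
- **Section 4.4, stopping treatment.** For a subject who "wants to discontinue treatment and agrees to the evaluations specified at the EOT/ET visit and/or at safety follow up", "the agreed assessments should be conducted".
- **Section 4.5.1, first sentence.** "Unless the subject (or parent/LAR) has withdrawn consent from all components of the study, every reasonable effort should be made to complete" the ET visit and the safety follow-up visit after premature discontinuation.
- **Section 3.1.2 and Table S-1 note b.** The safety follow-up is omitted only if consent to all parts of the study is withdrawn.
- **Table S-1 note n.** The ET visit is omitted on the same condition.
- **Section 6.6.** The 30-day telephone contact is due for completers and for those who discontinue prematurely. No exception is made for AEs.

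**The concern.** The sentence in 7.3 names a different trigger from the section it cites. It does not mention consent, and it turns on the reason for leaving (an AE) rather than on what the subject has refused. Section 7.3 is a natural place for a site to look when a child leaves because of an AE, and the sentence is worded as a prohibition.

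The primary endpoint is TEAEs, counted up to 30 days after the last dose (Protocol 9.5.1; SAP 14.1). A site that followed the sentence to the letter would skip the ET visit and the 30-day call for such a subject. That could lose the outcome of a non-serious AE, any non-serious TEAE starting after the subject left, and the ET safety measurements. Under SAP 5.3.3 and 5.3.4, ET values feed the by-visit summaries and the overall post-baseline extremes and potentially clinically important values. The subject would stay in the Safety Analysis Set, which needs only one dose, so events not collected would simply be absent from the counts.

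**Working it through.** No formula applies, and the plan states no figure on this point. The check is to set the rules side by side for each way in which a subject may leave.

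1. **Consent withdrawn from all components because of an AE.** Section 7.3 stops assessments, and so do 4.4, 3.1.2, 4.5.1 and Table S-1 notes b and n. They agree.
2. **Consent withdrawn from all components for another reason.** Section 4.4 stops assessments. The 7.3 sentence is silent. There is no conflict, but the words about an AE add nothing to 4.4: full withdrawal ends assessments whatever the reason.
3. **Study drug stopped because of an AE, subject stays in follow-up.** The 7.3 sentence speaks of withdrawing from the study, so on its own words it does not reach this subject. The treatment-stopping clause of 4.4 and the AE rule in 4.5.1 ("If a subject is discontinued from the study treatment because of an AE, every reasonable attempt should be made to follow and appropriately treat") apply. There is no conflict.
4. **Subject leaves the study because of an AE, without withdrawing consent from all components.** Section 7.3, read literally, bars every further assessment. The first sentence of 4.5.1 asks for reasonable effort to complete the ET visit and safety follow-up. Section 3.1.2 and Table S-1 notes b and n do not excuse either contact, and 6.6 requires the 30-day call. If the AE is ongoing, the preceding sentence of 7.3 also asks for follow-up. Here the texts conflict.

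Only case 4 is exposed. Compared with 4.4, the 7.3 sentence is wider on the type of withdrawal and narrower on the reason.

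For timing, the TEAE window closes at last dose + 30 days, and the call is due at 30 (+3) days, that is 30 to 33 days after the last dose. The call is therefore the scheduled contact that covers the window through to its end.

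Two things limit the loss even in case 4. The AE that led the subject to leave is already recorded and counted. Section 7.4.2 separately requires follow-up for serious AEs through the safety follow-up period.

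**The case against.** The strongest reply is that the sentence already means withdrawal of consent. It cites 4.4, which is titled for withdrawal of consent and itself opens with the subject's right to withdraw from the study. The consent text in 12.3.1 and 12.3.2 uses the same phrase. Section 7.3 uses the verb actively, with the subject as actor, and contrasts it with the sentence just before, on subjects who discontinue. A site would have to overlook that sentence, the cross-reference and the visit schedule to go wrong.

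Most of this stands. It makes full withdrawal of consent the likely intent and the correct practice recoverable. What it does not do is put the limit into the sentence. Section 4.4 describes two situations with different outcomes, and 7.3 does not say which it means. On the consent reading the mention of an AE has no function, so it invites a site to treat the AE as the trigger.

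Two further arguments might be drawn against the sentence, and neither is supported. A reader might infer from Section 4.5, which lists adverse event and withdrawal of consent as separate reasons, that leaving because of an AE cannot be a withdrawal of consent. That list gives reasons for stopping study treatment, so it does not settle what withdrawing from the study means. A reader might also see a clash with the treatment-stopping clauses of 4.4 and 4.5.1. Those concern stopping the drug, and the 7.3 sentence concerns leaving the study.

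**Conclusion.** The sentence is wrong as written. It is a wording fault in an operative safety rule, worth correcting at low priority. It is not a flaw in the design and not a proven conflict of intent.

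The effect is zero if every site reads the sentence through 4.4, which is the likely reading. It is above zero only if some site applies it literally to a subject who leaves the study because of an AE without withdrawing all consent. The loss would then be that subject's ET safety assessments and 30-day call, chiefly information on non-serious events. The documents give neither the share of subjects expected to leave in this way nor any sign of how sites would act, so no count is offered.

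A reader might infer that the protocol forbids follow-up of AE dropouts and that the primary safety results are therefore biased. The documents do not support this: every other rule on the point keeps the follow-up in place. Confidence is high for the gap in the wording. No effect on the primary endpoint has been shown.

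**What to change.** Replace the last sentence of Section 7.3 with:

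> If the subject (and/or parent/LAR) withdraws consent from all components of the study, including because of an AE, no additional assessments will be performed (Section 4.4). Otherwise, for a subject who leaves because of an AE, every reasonable effort should be made to complete the ET visit and safety follow-up to which the subject agrees, and to follow the AE (Sections 4.4, 4.5.1 and 6.6).

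This keeps the right to withdraw completely, the agreement condition of 4.4 and the reasonable-effort standard of 4.5.1. The cost is a clarification in one place. The ET visit and the 30-day call are already scheduled, and no endpoint or analysis changes.
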